Study Background	COVID-19 is a global pandemic. Preliminary data from pre-clinical studies and observations in humans suggest that the combination of chloroquine and azithromycin can suppress virus growth and reduce viral load in infected patients.
Study Aim	This program will determine whether the combination of chloroquine and azithromycin reduces the primary outcome of clinical progression of COVID-19. The program consists of 2 parallel trials in people who have tested COVID-19 positive; 1) the outpatient trial , and 2) the inpatient trial .
Study Population Main eligibility	1) Outpatient trial : Outpatients with a COVID-19 diagnosis (either individuals at screening clinics, in the emergency room but not admitted to hospital, or health care staff who have tested positive) and 2) Inpatient trial : Patients admitted to hospital with a diagnosis of COVID-19 infection.
criteria:	 Inclusion criteria 1) Age ≥ 18 years 2) Provision of informed consent 3) Diagnosis of active COVID-19 using established testing
	 Exclusion criteria 1) Known glucose-6-phosphate dehydrogenase (G6PD) deficiency 2) Contra-indication to chloroquine or azithromycin 3) Already receiving chloroquine or azithromycin
Study Outcomes	Outpatient trial A) Primary outcome: composite of hospital admission or mortality
	B) Secondary outcomes: 1) Mortality 2) Hospital admission 3) Invasive mechanical ventilation 4) Admission to intensive care unit (ICU) 5) Renal replacement therapy 6) Extracorporeal support
	C) Translational outcomes (in a subset of patients) 1) Viral titre 2) ACE-2 levels 3) Inflammatory markers
	D) Safety outcomes

	,
	 Malignant arrhythmia needing intervention Agranulocytosis Stevens-Johnson syndrome/toxic epidermal necrolysis Retinal toxicity
	2) Inpatient trial A) Primary outcome: composite of invasive mechanical ventilation or mortality
	B) Secondary outcomes: 1) Mortality 2) Invasive mechanical ventilation 3) Admission to ICU 4) Renal replacement therapy 5) Extracorporeal support
	C) Translational outcomes (in a subset of patients) 1) Viral titre 2) ACE-2 levels 3) Inflammatory markers
	D) Safety outcomes: 1) Malignant arrhythmia needing intervention 2) Agranulocytosis 3) Stevens-Johnson syndrome/toxic epidermal necrolysis 4) Retinal toxicity
Study Design	Open-label, randomized trials. A vanguard phase will start as soon as possible in Hamilton and nearby regions. Thereafter study will expand to other centers in Canada and other countries, as necessary and feasible.
Total number	1) Outpatient trial
of subjects:	Minimum total sample size required is N= 1000 (500 in each arm); it will provide 90% statistical power to detect a 50% relative risk reduction (RRR) in the proportion developing the primary outcome, assuming an usual care risk of progression of 12%.
	2) Inpatient trial
	Minimum total sample size required is N=530 (265 in each arm) in order to have 90% statistical power to detect a 40% RRR in the proportion progressing to mechanical ventilation or mortality, assuming an usual care risk of progression of 30%.

Study Intervention (both trials)

Patients will be randomly allocated to an active group that will receive chloroquine for a total of 7 days plus azithromycin for 5 days plus usual care **or** to usual care, as follows:

Chloroquine

Adults with a bodyweight \geq 50 kg: 500 mg twice daily for 7 days Adults with a bodyweight < 50 kg: 500 mg twice daily on days 1 and 2, followed by 500 mg once daily for days 3 -7

Azithromycin

500 mg on day 1 followed by 250 mg once daily for 4 days

Statistical Considerations

Randomization: In both trials, randomization will be done within center, in randomly permuted blocks.

Adaptive design features (both trials):

- Adaptive termination: A Data & Safety Monitoring Committee (DSMC) will follow a flexible pragmatic monitoring approach for efficacy and safety, considering each trial separately. They will review accumulating data after every 50 subjects have been randomized (with the ability to modify frequency of their review as dictated by the emerging data) and will only stop the trial if there is proof beyond reasonable doubt of efficacy (modified Haybittle-Peto boundary of 3 standard deviation (SD) for benefit or harm as a general guideline). They will also look for consistency of efficacy results across both trials prior to recommending early stopping for a trial.
- Adaptive intervention arms: The DSMC and the Study investigators will keep abreast of other ongoing trials and, if another promising intervention emerges, they may recommend adding (or replacing) one or more arms with the new promising intervention(s).
- Adaptive sample size: Sample size calculations are based on disease progression rates that are not well known. We remain flexible, and the DSMC will be monitoring the possibility that the assumptions for sample size calculations may be modified with emerging information from this trial or other ongoing trials. If necessary, sample size may be increased accordingly.

Analysis: The primary hypothesis of efficacy will be conducted under the intention-to-treat principle; all randomized participants will be included in the analyses. Each trial will be analyzed separately with 2-sided level of significance of 0.05. No modification of the level of significance is necessary with the 3 SD boundary for the Haybittle-Peto criteria.

Outpatient trial: The primary analysis will use the Z-test for comparison of proportions. Secondary analyses will include adjusting

	the intervention effect for demographic and exposure characteristics of the participants using logistic regression models.
	Inpatient trial: The primary analysis will use the Z-test for comparison of proportions. Secondary analyses will include adjusting the intervention effect for demographics, exposure characteristics, and severity of disease upon admission, using logistic regression models.
Duration of Study Period (per subject)	Patients will be followed for 45 days from randomization in both trials and will receive a telephone call at 1 year to evaluate vital status.

1. Program Background

A novel severe acute respiratory syndrome coronavirus 2 (SARS-CoV-2) has affected hundreds of thousands of people worldwide. The disease that is now known as COVID-19 was first reported to the World Health Organization on December 31, 2019. The disease is spreading quickly around the globe and has been declared a pandemic on March 11, 2020. Exploring therapies potentially of benefit for COVID-19 is a public health emergency.

Chloroquine and azithromycin in combination have shown promise in treating COVID-19. In vitro, chloroquine increases the endosomal pH required for the virus to fuse with cells, interferes with the glycosylation of SARS-CoV-2 cell receptors, thereby blocking viral infection. Investigators performed a time-of-addition assay which showed that chloroquine is effective at both the entry and post-entry stages of the SARS-CoV-2 infection in cells. Azithromycin is a macrolide antibiotic that has been found to inhibit the viral tropism and replication of Zika and Ebola viruses. 3-5

In a non-randomized, open label clinical experience of 36 patients, the combination of azithromycin and hydroxychloroquine was associated with a significant reduction in viral load and reduction of viral carriage by day 6 compared to controls. Patients treated with the combination of azithromycin and hydroxychloroquine also had shorter carrying duration compared to patients reported in the literature. In the subgroup of patients who were treated with azithromycin for clinical reasons, viral elimination was noted to be faster.

There is sparse information on the effects of both drugs in people with coronavirus infection and little or no clinical symptoms. Preventing clinical disease leading to hospitalizations is of great clinical and public health value. This has led some governments or their spokespersons (e.g., the US, India) to recommend the routine use of chloroquine as prophylaxis, We believe that evaluating the effects of these regimen in a well-designed randomized controlled trial is important, with careful attention to safety (avoiding the use of large loading doses, use of low doses for no more than 7 days), and telephone checks on clinical safety as in person assessments are not practical during this period where physical distancing is recommended) and regular monitoring of both efficacy and safety by an independent group of experts.

We assume hydroxychloroquine and chloroquine have similar anti-viral activity. We will refer to both drugs as chloroquine unless otherwise specified in this protocol (at present it is not known which of the above two drugs will be available in sufficient quantities to conduct the trial rapidly). Although chloroquine and azithromycin prolong the QT interval, it is very rarely associated with clinically important arrhythmias, and usually at higher doses than used in our study.⁷⁻⁹

The world needs several trials of existing agents that are repurposed to treat and prevent COVID-19 pneumonia and related complications. Of the currently known agents, chloroquine and azithromycin appear to be promising in the treatment for COVID-19.

Preventing people infected with COVID-19 from developing severe enough symptoms to require hospitalization is as important as treating people with COVID-19 pneumonia from deteriorating and needing ventilation or experiencing death. Therefore, we have established a program that includes two parallel trials; an **outpatient trial** seeking to prevent hospital admission and mortality, and an **inpatient trial** seeking to prevent need for mechanical ventilation or mortality. This program is a priority. If this therapy is proven conclusively to be effective, it will be used around the world. If it proves ineffective, other treatments will be explored emergently using the platform we (and other investigators) will establish.

As we design the trials, we acknowledge that many of the details usually available to design a study are not reliably available. This includes event rates (although we have made the best estimate using available data), potential size of the study or the numbers of cases that can be enrolled within a reasonable period as the number of cases is expected to increase rapidly in Canada and in many other countries). We have therefore designed these trials using the best available data, our judgement and with the goal of recruiting as many patients as possible (but at least 1000 into an outpatient trial and at least 530 into the inpatient trial). We have also built in two key mechanistic substudies testing the effects of the regimen on viral loads and on inflammation – to get an early indication of potential efficacy. During the conduct of the trials, we may need to make adjustments to several aspects of study design. To enable this and to monitor safety, the trial data will be reviewed periodically by an expert and independent data and safety monitoring committee (DSMC). We may also consider adding new arms or replacing existing arms (if they are shown to be ineffective based on emerging data) as promising new treatments emerge.

2. Program Hypothesis

Azithromycin in combination with chloroquine therapy (AZCT) on top of usual care will reduce disease progression of COVID-19 compared to usual care.

3. Outpatient trial: Preventing disease progression in COVID positive outpatients

3.1 Study Objectives

3.1.1 Primary objectives

To evaluate if AZCT compared to usual care results in reduced hospital admission or mortality for outpatients diagnosed with COVID-19.

3.1.2 Secondary efficacy objectives

To evaluate if AZCT compared to usual care results in reductions in mortality, hospitalization, invasive mechanical ventilation, admission to intensive care unit (ICU), renal replacement therapy, and extracorporeal support in outpatients diagnosed with COVID-19.

3.1.3 Tertiary efficacy objectives

To evaluate if AZCT compared to usual care results in reductions in length of ICU stay, length of hospital stay, non-invasive ventilation, and duration of ventilation.

3.1.4 Translational objective (in a subset of participants)

To evaluate if AZCT compared to usual care results in reductions of viral titre and inflammatory markers and to assess whether expression of ACE-2 levels is associated with mortality.

3.1.5 Safety objectives

To evaluate whether the risk of the following is increased in patients with COVID-19 receiving AZCT compared with those receiving usual care: malignant arrhythmia requiring intervention, agranulocytosis, Stevens-Johnson syndrome/toxic epidermal necrolysis, and retinal toxicity.

3.2 Study Design

3.2.1 Type of study

A multi-centre, open-label, parallel group, randomized controlled trial evaluating the efficacy and safety of AZCT plus usual care compared to usual care in outpatients with COVID-19.

3.2.2 Expected number of patients

The minimum sample size for the study is a total of 1000 outpatients. This sample size may change as this trial has an adaptive design.

3.2.3 Allocation procedure

Randomization: Eligible patients that have provided informed consent will be randomized via the central interactive web randomization system (IWRS) at the Population Health Research Institute. The process should take less than 3 minutes. Each patient will be assigned to one of two groups, AZCT plus usual care or usual care, in randomly permuted blocks (undisclosed sizes to maintain concealment of allocation). The allocation will be communicated to site personnel and patients will be made aware of their assignment. It is not practical to use placebo as this would entail considerable delays in starting the trial but the outcomes are likely to occur and be ascertained independent of the knowledge of the treatment allocation. Therefore, the results are likely to be unbiased.

Stratification: We will stratify randomization by site.

3.2.4 Duration of the study period for each subject

Patients will be followed for 45 days from the time of randomization. Data of events occurring in hospital will be obtained from hospital records supplemented by a telephone call or follow up at 7-10 days and at 45 days after randomization. Participants will receive a telephone call at 12 months to determine morbidity and mortality.

3.3 Study population

These patients will be identified at screening clinics and in emergency rooms. This group will also include healthcare workers screened for COVID-19 infection. They will be eligible once a diagnosis of COVID-19 is confirmed by established testing. These patients will not have been admitted to hospital at the time of enrolment.

3.3.1 Inclusion criteria

- 1) Age ≥ 18 years of age
- 2) Informed consent
- 3) Diagnosis of active COVID-19 confirmed by established testing

3.3.2 Exclusion criteria

- 1) Known glucose-6-phosphate dehydrogenase (G6PD) deficiency
- 2) Contra-indication to chloroquine or azithromycin
- 3) Already receiving chloroquine or azithromycin

3.3.3 Adaptive design features

Adaptive intervention arms: The DSMC and the Steering Committee will keep abreast of other ongoing trials and, if a more promising intervention is emerging, may recommend adding (or replacing) one arm with the new promising intervention. They will also assess the results of the translational objectives when available and may add a chloroquine loading dose if a rapid or large reduction in viral titres is not observed with the current regimen.

Adaptive sample size: Sample size calculations are based on disease progression rates that are not well known. The DSMC will monitor the possibility that the assumptions for sample size calculations may be modified with emerging information from this trial or other ongoing trials. If recruitment is going well, the steering committee may decide to extend recruitment as long as the independent DSMC does not terminate the trial for clear evidence of efficacy, futility (or low likelihood) to detect a clinically meaningful difference (e.g. a 20% RRR in events) or concerns about safety.

3.4 Study Procedures

In order to make it possible to implement this protocol where resources are scarce, we have simplified trial procedures, and data collection. Direct electronic data entry is encouraged.

3.4.1 Consenting process

These patients will be consented by a variety of strategies. These can include consent to be contacted in the future which will be obtained at the time of screening (i.e., before the results of testing are available) and consent to participate once a positive test result is received. In all cases, we will explain the trial, answer their questions and document the consent process.

3.4.2 Interventions

Blinding: Patients and healthcare providers will not be blinded to treatment. To account for this, we have objective outcome definitions to minimize the opportunity for bias to influence event assessment.

Consenting participants will be randomized to receive AZCT plus usual care or usual care.

AZCT Arm

Chloroquine

Adults with a bodyweight ≥ 50 kg: 500 mg twice daily for 7 days Adults with a bodyweight < 50 kg: 500 mg twice daily on days 1 and 2, followed by 500 mg once daily for days 3-7.

Azithromycin

500 mg on day 1 followed by 250 mg daily for 4 days

Usual Care

We will place no constraints for treating physicians with respect to usual care. We will document information on all key co-interventions, including information on drugs at the time of randomization and post randomization/during hospitalization.

3.4.3 Data collection

We will collect patient sex, age, disease severity, comorbidities (smoking, diabetes, heart disease, lung disease, immunosuppression, etc.), other medications, and trial outcomes. A minimum of 50 patients in this trial will be swabbed on days 0, 1, 3, 5, 7, 10, 14 for quantitative polymerase chain reaction (PCR) assessment of viral titre. In addition, a

subset of patients will have blood collected on the date of randomization and on day 3 for biomarker evaluation (targeted at markers of inflammation) and to biobank for later analysis.

3.5 Study Outcomes

3.5.1 Primary efficacy outcome

The primary outcome is admission to hospital or mortality.

3.5.2 Secondary efficacy outcomes

The secondary outcomes are mortality, admission to hospital, invasive mechanical ventilation, admission to ICU, renal replacement therapy, and extracorporeal support.

3.5.3 Tertiary efficacy outcomes

Tertiary outcomes are length of ICU stay, length of hospital stay, noninvasive mechanical ventilation, and duration of mechanical ventilation.

3.5.4 Translational outcomes

The translational outcomes are viral titre, ACE-2 levels and biomarkers.

3.5.5 Safety outcomes

The safety outcomes are malignant arrhythmia requiring intervention, agranulocytosis, Stevens-Johnson syndrome/toxic epidermal necrolysis, and retinal toxicity.

3.6 Safety outcome definitions

Malignant arrhythmia requiring intervention: Life-threatening ventricular arrhythmias: Regular, wide complex tachycardia lasting at least 30 seconds or associated with hemodynamic instability, polymorphic ventricular tachycardia (including torsades de pointes) of any duration, ventricular fibrillation of any duration requiring intervention.

Agranulocytosis: severe neutropenia, neutrophils below 500 cells/mm³ of blood.

Stevens-Johnson syndrome/Toxic epidermal necrolysis: fever, mucositis, skin tenderness, and blistering.

Retinal toxicity: New onset loss of vision with associated bilateral change of retinal pigmentation (Bull's-eye maculopathy).

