5.1.1 Serious adverse events

For the purposes of this trial, study efficacy and safety outcomes, known adverse effects of study medications, and events that are expected to occur with high frequency in patients with COVID-19 infection will be captured on the CRF and will be exempted from the expedited reporting. All of these events will be included in the final study report and reviewed by the DSMC on an ongoing basis.

Only those events that are both serious and unexpected for the patient population under study and who are being treated with study medication will be reported to the regulatory agency in an expedited manner.

Adverse events that are not serious, but which lead to permanent discontinuation of study medication will be recorded and included in the final study report.

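### The malignant arrhythmia outcome requires an identified rhythm, so a sudden death at home is counted only as all-cause mortality unless a rhythm was recorded

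*Protocol*

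**What the plan says.** Section 3.5.5 gives a closed list: "The safety outcomes are malignant arrhythmia requiring intervention, agranulocytosis, Stevens-Johnson syndrome/toxic epidermal necrolysis, and retinal toxicity". Section 4.5.5 gives the same four for inpatients.

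Section 3.6, repeated in 4.5.6, defines the arrhythmia outcome in limbs. The first is "Regular, wide complex tachycardia lasting at least 30 seconds or associated with hemodynamic instability". The rest are "polymorphic ventricular tachycardia (including torsades de pointes) of any duration, ventricular fibrillation of any duration requiring intervention".

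The Program Background acknowledges the mechanism of concern and plays down its frequency: "Although chloroquine and azithromycin prolong the QT interval, it is very rarely associated with clinically important arrhythmias". It also says that safety checks will be made by telephone, because seeing patients in person is impractical.

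Section 3.2.4 takes in-hospital events from hospital records, supplemented by a "telephone call or follow up at 7-10 days and at 45 days after randomization". Section 3.4.3 lists the data and samples to be collected for outpatients. No rhythm recording, blood count or eye examination is among them.

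Death enters the primary composite (3.5.1) and is a secondary efficacy outcome (3.5.2). Section 5.1.1 exempts "study efficacy and safety outcomes, known adverse effects of study medications" and events expected to be frequent in COVID-19 from expedited reporting. It keeps them in DSMC review and in the final report.

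**The concern.** The safety objective in 3.1.5 is to find out whether the treatment increases malignant arrhythmia, among other harms. The protocol names QT prolongation as a property of both drugs. The fatal form of that risk, outside hospital, is a sudden collapse that often leaves no tracing. Every limb of the definition names a rhythm, so such a death cannot meet it, and none of the other three safety outcomes would catch it.

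The comparison of arrhythmia by arm could then show few or no events in the outpatient trial, whatever the true effect on fatal arrhythmia. The deaths would still be visible in the mortality comparison, but mixed with deaths from COVID-19 and with no category to pick them out. Safety classifications that were never made are hard to recover reliably at analysis.

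**Working it through.** No figure in the protocol bears on this point, so there is none to reproduce. The check is to trace one event through the outcomes as written, then to illustrate the size under labelled assumptions.

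**Step 1. An outpatient dies suddenly at home with no rhythm recorded.**

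| Defined outcome | What it needs (3.6) | Met? |
|---|---|---|
| Malignant arrhythmia | One of the named rhythms; the outcome's title adds a need for intervention | No |
| Agranulocytosis | A neutrophil count below 500 | No |
| Stevens-Johnson syndrome / toxic epidermal necrolysis | Clinical signs | No |
| Retinal toxicity | Visual loss with bilateral pigment change | No |
| Primary composite, mortality (3.5.1, 3.5.2) | Death from any cause | Yes |

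If responders record one of the named rhythms, the event could qualify. A resuscitated arrest with no rhythm recorded, or with a rhythm not on the list, does not.

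**Step 2. Can the scheduled data supply a rhythm?** For outpatients the sources are hospital records and the contacts at days 7-10 and 45 (3.2.4), plus the items in 3.4.3. None supplies a rhythm for a patient who dies before reaching care. For inpatients, 4.2.4 makes hospital records the source, so a rhythm is more likely to be on file.

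**Step 3. What a misplaced event does to the tables (illustration).** Inputs are 500 per arm and planning risks of 12% and 6% (3.7.1 and the synopsis), ignoring loss to follow-up. The assumption, which is not in the protocol, is 3 unrecorded arrhythmic deaths in treated patients who would otherwise have had no primary event, with no other arrhythmias in either arm.

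- Planned result: 500 × 0.12 = 60 events v 500 × 0.06 = 30. The pooled proportion is 90/1000 = 0.090, so z = 0.060 / √(0.090 × 0.910 × 2/500) = 0.060 / 0.0181 = 3.3.
- With the 3 deaths: 60 v 33. The pooled proportion is 0.093, so z = 0.054 / √(0.093 × 0.907 × 2/500) = 0.054 / 0.0184 = 2.9.
- Arrhythmia row: 0 v 0 as defined. A sudden-death row would read 3 v 0, plus any background.
- Strength of 3 v 0 alone: the two-sided Fisher p is 2 × (500 × 499 × 498)/(1000 × 999 × 998) = 0.25.

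The composite absorbs the three deaths and still favours treatment. A separate row would not prove harm, but it would show the pattern.

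**Step 4. How incomplete recording weakens a zero (illustration).** Assume a true risk of malignant arrhythmia of 0.5% in 500 treated outpatients, so 2.5 cases are expected. If a share s of cases has a recorded rhythm, the chance of counting at least one is 1 − (1 − 0.005s)^500.

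| s | Chance of at least one recorded case |
|---|---|
| 1 | 91.8% |
| 0.5 | 71.4% |
| 0.25 | 46.5% |
| 0 | 0% |

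Zero events in 500 gives a one-sided 95% upper limit of 1 − 0.05^(1/500) = 0.60%, but only if every case would have been recorded.

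**Step 5. The other outcomes.** The definition "Agranulocytosis: severe neutropenia, neutrophils below 500 cells/mm³ of blood" needs a laboratory result, and retinal toxicity needs an examination as well as the symptom. Sections 3.4.3 and 4.4.3 list swabs and, in a subset, blood on the day of randomization and on day 3 for inflammatory and related markers or storage. Neither a neutrophil count nor a retinal examination is listed. The skin outcome rests on clinical signs and needs no test.

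**The case against.** The strongest reply is that no death is lost. All-cause mortality is compared by arm under intention-to-treat. Section 5.1 has adverse events collected systematically, with safety and outcome data reviewed by the independent DSMC and sent to regulators monthly. Section 5.7 lets the DSMC look at adverse events and other safety indicators, not only the four named outcomes. Mortality is also less open to bias in an open-label trial than a judgement that a death was sudden. All of this stands, and it limits the point to classification.

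A reader might infer more than the documents support:

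- *That a sudden death at home is never a safety matter, or that the DSMC is kept from seeing it.* The exemption in 5.1.1 concerns only the speed of regulatory reporting; the same section sends these events to the DSMC and to the final report.
- *That such deaths would mostly be put down to COVID-19.* The protocol describes no attribution of cause of death, so this is conjecture.
- *That all the other safety outcomes depend on unscheduled tests.* The skin outcome does not, and visual loss can be reported at a follow-up contact.

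It is also fair to say that the protocol simplified its procedures deliberately (3.4), and that denominators of patients tested can be left to the statistical analysis plan. Neither answers the main point: the outcome definitions are fixed in this document, and they leave out the form of the harm that outpatient follow-up is least able to document.

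**Conclusion.** The point holds in this form. Read exactly as written, the arrhythmia outcome can be met only with an identified rhythm, and no other defined safety outcome covers sudden death or cardiac arrest. An outpatient's sudden death at home without a recorded rhythm is counted as all-cause mortality and nothing more specific. It reaches the DSMC but is not distinguished from other deaths. The effect falls mainly on the outpatient trial.

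The size cannot be taken from the protocol, which gives no arrhythmia rate and describes clinically important arrhythmias as very rare. The three deaths, the 0.5% risk and the recording shares above are assumptions that show direction, not estimates. The conclusion rests on the text of 3.5.5 and 3.6 and on the absence of rhythm recording from 3.4.3. It is a weakness in an outcome definition and worth correcting. It is not a contradiction, and it does not affect the validity of the efficacy comparison.

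A secondary point: zero counts of agranulocytosis and retinal toxicity should be read as none clinically detected, not as evidence of absence.

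**What to change.** 1. In 3.6 and 4.5.6, and in the lists in 3.5.5 and 4.5.5, add a separate safety category: *sudden or unexplained death, or resuscitated cardiac arrest, with or without a recorded rhythm*. Keep it distinct from documented malignant arrhythmia so that the specific outcome is not diluted.
2. Define it by objective criteria (timing, setting, no other documented cause), because the trial is open-label. Classifying the deaths without sight of the allocation would strengthen this further.
3. Record syncope at the existing contacts at days 7-10 and 45.
4. Tabulate the new category and syncope by arm, beside all-cause mortality.
5. State that zero counts of agranulocytosis and retinal toxicity mean none clinically detected.

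The cost is some outcome wording, a question at contacts already planned and a field on the death form. No dose, schedule or treatment rule changes. The downside is that some sudden deaths from COVID-19 will be counted in both arms, which adds noise; showing all-cause mortality alongside keeps the comparison interpretable.
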